1.2.3 Clinical Activity

Phase I open-label, dose-escalating study pharmacokinetics

ESK981 was tested in an open-label dose-escalating Phase 1 clinical trial to determine its pharmacokinetics (PK) and pharmacodynamics (PD) in patients with advanced, relapsed, or refractory solid tumors (Study C11981/1047/ON/US, NCT00875264) [31]. After daily oral administration of ESK981 to cancer patients, the median t_{max} values for ESK981 were typically in the range of 2 to 4 hours (Table 1 and Table 2). However, for most of the dose groups there appeared to be considerable inter-patient variability in this pharmacokinetic parameter. The reason(s) for the large inter-patient variability in t_{max} is(are) not presently known, but may be related to the fed/fasted state of the patients or other unknown factors which could potentially influence drug absorption (e.g., disease state, concomitant medications).

Table 1. Mean (SD) Pharmacokinetic Parameters for SK981 in Cancer Patients on Day 1 of Daily Oral Administration of ESK981

Dose (mg/m ²)	C _{max} (ng/mL)	t _{max} ^a (hr)	AUC ₀₋₂₄ (ng·hr/mL)	AUC _{0-∞} (ng·hr/mL)	t _{1/2} (hr)	R _{pred}
3.0 (n=3)	13.7 (6.1)	6.0 [2.0-6.1]	127 (16)	151 (36)	8.0 (2.8)	1.2 (0.2)
4.2 (n=3)	16.8 (4.9)	4.0 [1.0-6.0]	119 (14)	136 (6)	7.8 (3.7)	1.2 (0.1)
5.9 (n=5)	26.0 (6.5)	2.1 [1.5-4.0]	195 (67)	210 (78)	5.9 (1.1)	1.1 (0.1)
11.8 (n=3)	84.9 (23.0)	1.6 [1.5-3.0]	517 (126)	569 (196)	6.0 (3.7)	1.1 (0.1)
19.7 (n=3)	135.7 (76.5)	4.0 [1.0-4.3]	874 (358)	928 (408)	5.1 (1.3)	1.0 (0.1)
29.6 (n=4)	266.9 (182.0)	2.3 [1.0-3.1]	2376 (2064)	3195 (3199)	8.5 (5.5)	1.2 (0.2)
41.4 (n=3)	351.9 (94.4)	2.0 [1.0-4.0]	2820 (2070)	3572 (3177)	8.1 (4.5)	1.2 (0.2)
55.0 (n=4) ^b	272.6 (127.5)	3.0 [3.0-3.2]	2274 (666)	2675 (508)	8.9 (2.5)	1.2 (0.1)
73.0 (n=3)	444.2 (149.4)	4.0 [3.0-4.1]	3939 (1966)	4659 (2634)	8.1 (2.2)	1.2 (0.1)
97.4 (n=9)	526.4 (185.7)	4.0 [2.0-6.0]	5320 (1459)	6915 (2115)	10.3 (4.6)	1.3 (0.3)
126.6 (n=2)	751.2 (780.5, 721.9)	5.0 [8.0, 2.0]	5767 ^d	NC	NC	NC
Overall Mean ^c	-	-	-	-	8.0 (3.7)	1.2 (0.2)

^aValues presented for t_{max} are the median [range]; ^bExcludes data from patient 1019 due to receipt of improper dose of study medication; ^cOverall mean for all dose groups; ^dn=1.

NC: Not calculable.

R_{pred} = AUC_{0-∞}/AUC₀₋₂₄.

Table 2. Mean (SD) Pharmacokinetic Parameters for ESK981 in Cancer Patients on Day 15 of Daily Oral Administration of ESK981

Dose (mg/m ²)	C _{max} (ng/mL)	t _{max} ^a (hr)	AUC _T (ng·hr/mL)	t _{1/2} (hr)	R _{obs}	R _{ss}
3.0 (n=3)	16.1 (2.3)	2.9 [1.5-4.0]	165 (83)	8.0 (2.9)	1.3 (0.6)	1.1 (0.5)
4.2 (n=3)	24.3 (9.2)	3.9 [1.5-4.0]	202 (47)	9.9 (4.6)	1.8 (0.6)	1.5 (0.4)
5.9 (n=5)	32.4 (8.4)	3.0 [1.5-6.0]	278 (69)	6.6 (1.5)	1.5 (0.6)	1.4 (0.6)
11.8 (n=3)	98.1 (5.6)	2.0 [1.6-2.1]	764 (128)	12.3 (9.7)	1.5 (0.2)	1.4 (0.3)
19.7 (n=3)	128.5 (98.4)	4.0 [1.5-4.0]	1102 (735)	5.4 (1.2)	1.2 (0.3)	1.1 (0.2)
29.6 (n=4)	218.8 (130.3)	4.5 [2.0-8.0]	2924 (2940)	8.7 (5.7)	1.1 (0.2)	0.9 (0.1)
41.4 (n=3)	412.6 (93.9)	2.1 [1.7-3.1]	3256 (1816)	10.3 (6.3)	1.3 (0.5)	1.1 (0.5)
55.0 (n=4) ^b	320.7 (75.1)	5.2 [3.0-8.0]	4313 (1091)	12.8 (4.3)	1.9 (0.2)	1.6 (0.1)
73.0 (n=2)	713.0 (734.5, 691.6)	3.3 [3.5, 3.1]	9429 (12253, 6605)	13.9 (20.6, 7.2)	1.9 (2.0, 1.8)	1.7 (1.6, 1.7)
97.4 (n=7)	7431.3 (336.7)	2.7 [1.5-6.0]	6623 (3283) ^d	11.0 (6.2) ^d	1.5 (0.9) ^d	1.2 (0.7) ^d
126.6 (n=1)	1481.5	8.0	23565	14.7	NC	NC
Overall Mean ^d	-	-	-	9.9 (5.3)	1.5 (0.5)	1.3 (0.5)

^aValues presented for t_{max} are the median [range]; ^bExcludes data from patient 1019 due to receipt of improper dose of study medication; ^cOverall mean for all dose groups; ^dn=1.

R_{obs} = AUC_T/AUC₀₋₂₄, day 1.

R_{ss} = AUC_T/AUC_{0-∞}, day 1.

After reaching peak plasma levels, ESK981 declined in a bi-phasic manner that was characterized by an initial phase of drug distribution and a slower terminal elimination phase. For some profiles, however, only the later phase was evident due to what appeared to be a more prolonged period of drug absorption. The mean t_{1/2} of the terminal elimination phase was generally in the range of approximately 8 to 10 hr; however, the values tended to be slightly larger after multiple doses at the higher dose levels (i.e., doses \geq 55 mg/m²) (Table 1 and Table 2).

The systemic exposures (i.e., C_{max} and AUC) of patients to ESK981 generally increased with increasing dose across the dose range evaluated on both days 1 and 15 (Table 1 and Table 2). There were some dose groups for which the mean values of C_{max} and AUC did not show an increase relative to the values from the preceding 1 or 2 dose levels; however, this result was not surprising given the

large inter-patient variability and the fact that most dose increments were less than 40%. Nonetheless, the overall results obtained are not suggestive of the presence of any obvious non-linearity in absorption and/or elimination of ESK981 in this dose range.

After once-daily administration of ESK981 at doses ranging from 3.0 to 126.6 mg/m², there was a small to moderate amount of accumulation of the compound in plasma at each dose level. The overall mean observed accumulation ratio (R_{obs}) for ESK981 was 1.5 (range = 1.1 to 1.9), which was slightly larger than the value predicted from the single-dose data (overall mean R_{pred} = 1.2; range = 1.0 to 1.3) (Table 1 and Table 2). Although the mean R_{obs} was slightly larger than the R_{pred} , this is not believed to be a strong indication of the presence of any time-dependent pharmacokinetic processes.

1.2.4 Clinical safety and efficacy

Adverse events

All 43 patients experienced ≥ 1 adverse event, and 38 patients (88.3 %) were deemed to have had adverse events possibly, probably, or definitely related to study drug. The most frequently reported adverse event of any grade was fatigue (n= 22, or 51 %). Other frequently reported adverse events (≥ 20 % of patients) were nausea (47 %), diarrhea (33 %), decreased appetite (33 %), abdominal pain (30 %), back pain (28 %), vomiting (28 %), constipation (28 %), headache (28 %), dizziness (28 %), and dyspnea (23 %). These adverse events were reported at a similar frequency between dosage cohorts, and no relationship with dose was evident. Most adverse events were grade 1 or grade 2. Grade 3 or 4 adverse events occurred in 16 (37 %) patients across dosing cohorts (14 [32.6 %] Grade 3 and Grade 2 [4.7 %] Grade 4). Treatment-related grade 3 or 4 adverse events were most frequent in the 97.4 mg/m² cohort. Grade 3 or 4 laboratory hematologic toxicities were reported in 8 (18.6 %) patients across dosage cohorts. The most common grade 3 or 4 laboratory hematologic toxicity was lymphopenia, which occurred in 8 patients and across dosage cohorts (5.9, 29.6, 55.0, 97.4, and 126.6 mg/m²). Grade 4 leukopenia occurred in 1 patient in the 126.6 mg/m² cohort. Grade 3 or Grade 4 neutropenia also occurred in 2 patients in the 97.4 mg/m² cohort (Grade 3) and in 1 patient in the 126.6 mg/m² cohort (Grade 4).

[figure not shown]
Serious adverse events occurred in 12 patients; most were deemed unlikely or not related to CEP-11981. Three patients (1 patient in the 97.4 mg/m² cohort and 2 patients in the 126.6 mg/m² cohort) experienced serious adverse events that were categorized as possibly or definitely related to ESK981: pyrexia, hemolytic anemia, hyperbilirubinemia, dyspnea, neutropenia, ECG change, and chest discomfort. No deaths occurred during the study.

Tumor response

Of 43 patients who received ≥ 1 dose of study drug, 37 patients were evaluated for tumor response. Although no enrolled patients had complete or partial response according to RECIST criteria, 19 of 37 (51 %) patients evaluated for tumor response had stable disease at ≥ 6 weeks; 18 had disease progression. The frequency of stable disease (defined as <30 % decrease and <20 % increase in the sum of the longest diameter of the target lesions) was higher in cohorts receiving doses ≥ 73.0 mg/m² (8 of 14 [57.1 %] patients) compared with cohorts receiving ≤ 55.0 mg/m² (11 of 29 [37.9 %] patients) (Figure 14).

Figure 14. Best overall tumor response per cohort^a at >/= 6 weeks

Depicts tumor response, with bars above the x-axis indicating patients (n = 19) who achieved stable disease and bars below the x-axis indicating patients (n = 18) with disease progression. ^aNo patient achieved complete or partial response. ^bSix patients were not evaluable at dosages of 19.7, 29.6, 55.0, and 126.6 mg/m² (n = 1, each); 97.4 mg/m² (n = 2)

1.3 Rationale

ESK981 monotherapy

ESK981 has cleared a dose-escalating phase I clinical trial and demonstrated favorable pharmacokinetics and pharmacodynamics in patients with advanced, relapsed, or refractory solid tumors with up to 85% of patients achieving stable disease at doses ≥ 73.0 mg/m².

ESK981 is an orally active multi-targeted receptor tyrosine kinase inhibitor that inhibits the human receptor for Angiopoietin-1 and Angiopoietin-2 (TIE-2), vascular endothelial growth factor receptor-2 (VEGFR-2), vascular endothelial growth factor receptor-1 (VEGFR-1), and fibroblast growth factor receptor-1 (FGFR-1) receptor tyrosine kinases. In addition to its effects on the angiogenesis promoting receptors VEGF and TIE-2, ESK981 treatment also induced robust cellular vacuolization indicative of cell death by autophagy, a mechanism not observed with other multiple tyrosine kinase inhibitors like crizotinib and cabozantinib.

A phase 1 study has shown the compound to be safe and tolerable [31]. The most frequently reported adverse event of any grade was fatigue (n = 22, or 51%). Other frequently reported adverse events (≥ 20 % of patients) were nausea (47 %), diarrhea (33 %), decreased appetite (33 %), abdominal pain (30 %), back pain (28 %), vomiting (28 %), constipation (28 %), headache (28 %), dizziness (28 %), and dyspnea (23 %). These adverse events were reported at a similar frequency between dosage cohorts, and no relationship with dose was evident. Most adverse events were grade 1 or 2. Although no enrolled patients had complete or partial response according to RECIST criteria, 19 of 37 (51 %) patients evaluated for tumor response had stable disease at ≥ 6 weeks. Of note, the majority of patients on this trial had tumor types that have been historically refractory to TKIs. The 0% response rate is similar to response rates seen when other VEGF-TKIs have been tried in non-kidney cancers such as colorectal cancer [33].

Given the significant pre-clinical rationale for use of an Ang-2 inhibitor in renal cell carcinoma that has become resistant to VEGF inhibition and the safety shown in a prior phase 1 trial, we propose a single center phase 2 trial of ESK981 in patients with metastatic renal cell carcinoma who have progressed despite treatment with a VEGF-TKI.

Nivolumab in renal cell carcinoma

Nivolumab (Opdivo) a PD-1 antibody, is FDA approved for the treatment of advanced renal cell carcinoma after disease progression on prior anti-angiogenic therapy. In the CHECKMATE-025 trial, nivolumab demonstrated improved overall survival compared with everolimus in the randomized clinical trial setting (25 months vs 19.6 months, HR 0.73, p-value 0.0018) [34].

ESK 981 in combination with anti-PD1 immunotherapy

VEGF inhibition in combination with immunotherapy in the form and anti-PD1 or anti-PD-L1 therapy has already been demonstrated in other drug combinations. Bevacizumab, an anti-VEGF therapy, in combination with atezolizumab (anti-PD-L1), was studied in ten patients with previously untreated metastatic RCC, and was well-tolerated. In this small cohort, there were 4 partial responses and 4 patients with stable disease [35]. A randomized multi-arm phase III clinical trial is currently ongoing evaluating the combination of lenvatinib, a multikinase inhibitor, with either everolimus or pembrolizumab compared with sunitinib in patients with advanced renal cell carcinoma (NCT02811861).

Given the superior activity of ESK981 compared to other small molecule VEGFR inhibitors especially potent inhibition of Tie-2 and additional autophagy inducing activity of ESK981, and the emerging clinical data on synergy between VEGFR inhibition and anti-PD1/L1 antibody immunotherapy, we propose a two-cohort phase II study. We first seek to evaluate the safety of ESK981 monotherapy in a safety cohort of 11 patients (Cohort A), after which accrual of Cohort B will begin, with a safety lead-in of six patients to establish a safe dose of ESK981 in combination with flat dose nivolumab at 480 mg IV. Subsequently, an expansion of Cohort B will be accrued to evaluate the clinical efficacy of the combination of ESK981 at the previously established safe dose in conjunction with nivolumab. Subjects in cohort A cannot cross-over into Cohort B.

2.0 STUDY OBJECTIVES AND ENDPOINTS

2.1 Primary Objective

- 2.1.1 To determine the clinical efficacy of ESK981 in combination with nivolumab therapy in patients with metastatic renal cell carcinoma.

2.2 Secondary Objectives

- 2.2.1 To assess the clinical efficacy of ESK981 monotherapy in patients with metastatic renal cell carcinoma.
- 2.2.2 To determine the safety and tolerability of ESK981 monotherapy and in combination with nivolumab in patients with metastatic renal cell carcinoma.

2.3 Exploratory Objective

- 2.3.1 To determine the quality of life of patients enrolled on the study as reflected in patient-reported outcomes.

2.4 Primary Endpoint

2.4.1 To assess the objective response rate (complete response and partial response) by RECIST 1.1 in metastatic renal cell cancer to the combination of ESK981 and nivolumab therapy.

2.5 Secondary Endpoints

2.5.1 To assess the objective response rate (complete response and partial response) by RECIST 1.1 in metastatic renal cell cancer to ESK981 monotherapy.

2.5.2 To determine frequency and severity of adverse events by CTCAE criteria of ESK981 in patients with metastatic renal cell carcinoma.

2.5.3 To evaluate secondary efficacy measures such as overall survival, progression free survival, duration of therapy, duration of response to ESK981 monotherapy in Cohort A and to the combination in Cohort B; response by combined RECIST v1.1 and irRECIST and irRECIST progression free survival (Cohort B only).

2.6 Exploratory Endpoint

2.6.1 Health-related quality of life assessment changes from baseline using EuroQoL-5D will be described using descriptive statistics.

3.0 PATIENT ELIGIBILITY

Subjects must meet all of the inclusion and exclusion criteria to be enrolled to the study. Study treatment may not begin until a subject is enrolled. No eligibility waivers will be granted for this clinical trial.

3.1 Inclusion Criteria

3.1.1 Histologic diagnosis of renal cell carcinoma (any histology except medullary carcinoma or collecting duct carcinoma is acceptable) with radiologic or histologic evidence of metastatic disease.

3.1.2 Prior treatment with up to one (and only one) anti-VEGF or VEGFR inhibitor (small molecule or antibody).

3.1.3 Must have measurable disease as per Response Evaluation Criteria in Solid Tumors, version 1.1 (RECIST 1.1) criteria.

3.1.4 Must be of age \geq 18 years at time of informed consent.

3.1.5 Ability to understand and the willingness to sign a written informed consent.

3.1.6 Karnofsky performance status \geq 60.

3.1.7 Most recent systemic therapy or most recent radiation therapy \geq 2 weeks of first study drug dose.

3.1.8 Recovery to baseline or \leq Grade 1 CTCAE v.4.03 from toxicities related to any prior treatments, unless AE(s) are clinically non-significant and/or stable on supportive therapy.

3.1.9 Women of childbearing potential must have a negative serum or urine pregnancy test within 28 days prior to prior to registration. Women of non-childbearing potential are defined as those who have no uterus, ligation of the fallopian tubes, or permanent cessation of ovarian function due to ovarian failure or surgical removal of the ovaries. All others are considered women of child bearing potential.

3.1.10 Adequate organ and marrow function as defined below:

System	Laboratory Value
Hematological	
Absolute Neutrophil Count (ANC)	$\geq 1.5 \text{ K/mm}^3$
Hemoglobin (Hgb)	$\geq 9 \text{ g/dL}$
Platelets (Plt)	$\geq 100,000/\text{mm}^3$
Renal	
Calculated creatinine clearance	Serum creatinine \leq 1.5 times the upper limit of normal OR creatinine clearance $>30\text{mL/min}$ by Cockcroft-Gault formula
Hepatic	
Total Bilirubin	$\leq 1.5 \times$ upper limit of normal (ULN)
Aspartate aminotransferase (AST)	$\leq 2.5 \times$ ULN ($\leq 3 \times$ ULN with known hepatic metastases)
Alanine aminotransferase (ALT)	$\leq 2.5 \times$ ULN ($\leq 3 \times$ ULN with known hepatic metastases)
Prothrombin time (PT) and activated partial thromboplastin time (aPTT) levels	$\leq 1.5 \times$ ULN (If patient is receiving anticoagulation that is expected to alter these levels, should be in targeted therapeutic range for that agent)

3.2 Exclusion Criteria

- 3.2.1 Prior treatment for metastatic disease with >1 anti-VEGF/VEGFR inhibitor.
- 3.2.2 Prior treatment with anti-PD/PD-L1/CTLA4/IDO antibody (for Cohort B patients only) or ESK981 (for Cohort A and Cohort B patients).
 - Prior mTOR inhibitors or glutaminase inhibitors are allowed.
- 3.2.3 Untreated brain metastases or spinal cord compression.
 - Patients with suspected or known treated brain metastases at screening should have a MRI (preferred) or CT preferably with IV contrast of the brain prior to study entry. Patients whose brain metastases have been treated may be considered if they have completed their treatment for brain metastasi(es) at least 4 weeks prior to study registration AND they show radiographic and clinical stability (by CT or MRI brain imaging, obtained after treatment to the brain metastases). In addition, any neurologic symptoms that developed either as a result of the brain metastases or their treatment must have resolved or be stable without the use of steroids at daily doses greater than 10 mg prednisone or equivalent for at least 14 calendar days prior to the start of treatment.
- 3.2.4 Uncontrolled hypertension defined as blood pressure $>150/90$ despite at least 2 anti-hypertensive medications as assessed by 2 blood pressure readings taken at least 1 hour apart during screening
- 3.2.5 Major surgical procedure or significant traumatic injury within 6 weeks prior to study registration. (>6 weeks prior to registration is permitted as long as they have fully recovered from any such procedure).

- 3.2.6 History of another primary malignancy except for: malignancy treated with curative intent and no known active disease for ≥ 2 years, adequately treated non-melanoma skin cancer without current evidence of active disease, adequately treated carcinoma in situ without current evidence of active disease, Gleason ≤ 6 prostate cancer.
- 3.2.7 Angina, myocardial infarction symptomatic congestive heart failure, cerebrovascular accident, transient ischemic attack, arterial embolism, pulmonary embolism, percutaneous angioplasty or Coronary arterial bypass surgery within the past 3 months.
- 3.2.8 History of gastrointestinal perforation or fistula in the past 6 months, or while previously on antiangiogenic therapy, unless underlying risk has been resolved (e.g. through surgical resection or repair).
- 3.2.9 The patient has known hypersensitivity to gelatin or lactose monohydrate.
- 3.2.10 The patient has received any investigational drug within 28 days prior to registration or 5 half-lives of the investigational drug, whichever is shorter.
- 3.2.11 History of bleeding disorders (e.g. pulmonary hemorrhage, significant hemoptysis, menometrorrhagia not responding to hormonal treatment) ≤ 6 weeks before Cycle 1 Day 1.
- 3.2.12 The patient is on a chronic daily medication known to be a severe or moderate inhibitor or inducer by Micromedex of CYP1A2, CYP2C8, or CYP3A4 at registration.
- 3.2.13 Systemic corticosteroids greater than the equivalent of 10 mg of prednisone or equivalent alternative steroid (except physiologic dose for adrenal replacement therapy) or other immunosuppressive agents (such as cyclosporine or methotrexate) and any other medications that could potentially impact the efficacy or safety of the study as judged by the treating investigator are NOT permitted from time of registration to subjects completing protocol therapy unless clinically indicated to manage adverse events or life threatening or serious conditions as determined by the treating investigator.
- 3.2.14 Have any condition that, in the opinion of the investigator, would compromise the ability of the subject to meet or perform study requirements.

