Exclusion Criteria	
 • Prior treatment for metastatic disease with >1 anti-VEGF/VEGFR inhibitor. • Prior treatment with anti-PD/PD-L1/CTLA4/IDO antibody (for Cohort B patients only) or ESK981 (for Cohort A and Cohort B patients). 
 ◦ Prior mTOR inhibitors or glutaminase inhibitors are allowed. • Untreated brain metastases or spinal cord compression. 
 ◦ Patients with suspected or known treated brain metastases at screening should have a MRI (preferred) or CT preferably with IV contrast of the brain prior to study entry. Patients whose brain metastases have been treated may be considered if they have completed their treatment for brain metastasi(e)s at least 4 weeks prior to study registration AND they show radiographic and clinical stability (by CT or MRI brain imaging, obtained after treatment to the brain metastases). In addition, any neurologic symptoms that developed either as a result of the brain metastases or their treatment must have resolved or be stable without the use of steroids at daily doses greater than 10 mg prednisone or equivalent for at least 14 calendar days prior to the start of treatment. • Uncontrolled hypertension defined as blood pressure >150/90 despite at least 2 anti-hypertensive medications as assessed by 2 blood pressure readings taken at least 1 hour apart during screening. • Major surgical procedure or significant traumatic injury within 6 weeks prior to study registration (> 6 weeks prior to registration is permitted as long as they have fully recovered from any such procedure). • History of another primary malignancy except for: malignancy treated with curative intent and no known active disease for ≥ 2 years, adequately treated non-melanoma skin cancer without current evidence of active disease, adequately treated carcinoma in situ without current evidence of active disease, Gleason ≤ 6 prostate cancer. • Angina, myocardial infarction symptomatic congestive heart failure, cerebrovascular accident, transient ischemic attack, arterial embolism, pulmonary embolism, PTCA or CABG within the past 3 months.

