5.0 TREATMENT PLAN

5.1 Treatment Dosage and Administration

Protocol treatment must start within 14 business days of enrollment to the study.

There are 2 cohorts for accrual with Cohort A being accrued first. Cohort B will follow and will have 2 stages of accrual. Cohort A will accrue 11 patients to ESK981 monotherapy treatment. Then Cohort B (combination therapy) will begin accrual of 17 patients to the first stage and if the interim analysis permits, the second stage will accrue an additional 19 patients.

5.1.1 Therapy with ESK981 will include starting dose of 160 mg (4 capsules) PO daily for 5 consecutive days followed by a 2-day off drug in each week, repeated weekly in 28 day cycles. Patients will continue treatment until disease progression or intolerable toxicity.

REGIMENT DESCRIPTION					
Agent	Premedications; Precautions	Dose	Route	Schedule	Cycle Length
ESK981	n/a	160 mg	PO	Once daily for 5 consecutive days of every week (5 days on followed by 2 days off)	28 days
Nivolumab (solution for injection)	Per institutional guidelines, none mandated.	480 mg/dose	IV infusion over 30-60 minutes with a sterile, nonpyrogenic, low protein binding 0.2 to 1.2 micrometer in-line filter. Follow with saline flush.	Day 1	28 days

Dose Level	Dose of ESK981	Dose of Nivolumab
Level 0	160 mg	Fixed at 480 mg flat dose
Level -1	120 mg	Fixed at 480 mg flat dose
Level -2	80 mg	Fixed at 480 mg flat dose

Dose-Limiting Toxicity (DLT)

Dose limiting toxicity (DLT) will be defined as any Grade 3 or higher toxicity (as defined by CTCAE 4.03) that occurs during the DLT evaluation period (Cycle 1 i.e. 28 days) EXCEPT laboratory abnormalities that are not clinically relevant or significant.

Subjects will be given a pill diary and instructed to complete it every cycle. Doses missed by 6 or more hours or vomited will be skipped and not made up but will be recorded on the diary as missed or vomited. The subject will be advised not to take any additional doses, but to wait for the next scheduled dose.

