6.0 SCHEDULE OF ASSESSMENTS

6.1 Time and Events Table

1 cycle (C) = 28 days (D).

Trial Period	Screening (-28 to -1 days)	C1D1	C2D1	C3D1	C4D1	Additional Cycles...	EOT ⁷	Follow-Up ⁸
							30 days from last dose (+/- 7 business days)	Every 12 weeks (+/-14 business days) for up to 24 months/death
Informed Consent	X							
Tumor tissue specimen (15 FFPE slides required; blocks preferred) identified	X							
Blood for banking		X						
History, PE, Concomitant Meds, Vital Signs ¹	X	X	X	X	X	X	X	
PT/INR, aPTT	X							
Karnofsky Performance Status	X	X	X	X	X	X	X	
Pregnancy Test for WOCBP ²	X							
Toxicity (include DLT) Evaluations ¹²	X	X	X	X	X	X	X	
CBC with differential, platelets ³	X	X ¹³	X ¹³	X	X	X	X	
COMP ⁴	X	X	X	X	X	X	X	
TSH	X	Every 12 weeks from Cycle 1 Day 1 ⁵						
QoL (EQ-5D-5L)		X	X	X		X ¹⁴		X
Pill Diary collection/handing out		X	X	X	X	X		
Tumor response assessment ⁶ (CT chest, CT or MRI abdomen/pelvis; CT or MRI brain if clinically indicated)	X			X		X ⁶		X
Treatment								
ESK98 ^{9, 10} (Cohort A and B)		X	X	X	X	X		
Nivolumab ¹¹ (Cohort B only)		X	X	X	X	X		
Survival Status								X

1. Vital signs will include weight, temperature, pulse, respirations, blood pressure; height will be obtained at screening only.
2. WOCBP: Women of child bearing potential; either urine or serum pregnancy test.
3. CBC with diff includes total WBC, hemoglobin, hematocrit and differential of the WBC including absolute counts. Other checks are at discretion of treating investigator.

4. COMP or Comprehensive metabolic profile includes sodium, potassium, chloride, bicarbonate, BUN, creatinine, AST, ALT, alkaline phosphatase, total bilirubin.
5. TSH: Every 12 weeks from Cycle 1 Day 1 (i.e. Cycle 4 Day 1; Cycle 7 Day 1, etc.).
6. Window of +/- 7 business days. Imaging will be with or without intravenous contrast, before or on associated visit. CT or MRI brain with (preferred) or without IV contrast if suspected or known brain metastases. Frequency of tumor assessments will be q2 cycles (i.e. q 8 weeks) for first 4 assessments beyond baseline and then q 3 cycles (i.e. 12 weeks) subsequently until withdrawal of consent/death/2 years from C1 D1 whichever is later. If CR/PD, should be confirmed with repeat imaging after an interval of at least 4 weeks. In follow-up, if subjects are on alternative therapies, no mandated imaging but data from routine imaging will be captured at least every 12 weeks if available (+/- 7 business days).

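### The blood pressure exclusion (3.2.4 and synopsis) applies only to patients already on two or more antihypertensives; the same or a higher pressure on none or one meets no blood pressure criterion

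*Combined protocol and SAP*

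**What the plan says.** The synopsis gives the exclusion as "Uncontrolled hypertension defined as blood pressure >150/90 despite at least 2 anti-hypertensive medications". Section 3.2.4 has the same wording, with the pressure judged "despite at least 2 anti-hypertensive medications as assessed by 2 blood pressure readings taken at least 1 hour apart during screening". Section 3.0 adds: "No eligibility waivers will be granted for this clinical trial".

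Two other criteria could touch a patient with high pressure. Inclusion criterion 3.1.8 requires recovery from "toxicities related to any prior treatments, unless AE(s) are clinically non-significant and/or stable on supportive therapy". Exclusion criterion 3.2.14 covers any condition that, in the investigator's opinion, "would compromise the ability of the subject to meet or perform study requirements".

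The Time and Events Table (6.1) schedules vital signs, including blood pressure, at screening and on Cycle 1 Day 1 (C1D1). It attaches no limit to either reading.

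**The concern.** An entry limit on blood pressure normally keeps the higher pressures out. Here the limit depends on how many drugs the patient already takes, so it can exclude the lower of two pressures and pass the higher. The sponsor evidently regarded 150/90 as a pressure that matters at entry, and asked for two separate readings to establish it. Yet the limit does not reach patients with the same pressure and less treatment.

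What is at stake is the safety of patients starting ESK981, which section 1.2.1 describes as a potent inhibitor of VEGFR-1 and VEGFR-2. Consistency also matters: the two sites complete an eligibility worksheet that the Coordinating Center reviews (section 4.0), and a worksheet that follows 3.2.4 carries the same gap.

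**Working it through.** The plan gives no figure to reproduce. The check is one of logic and of coverage.

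**Step 1: the rule as a condition.** Because 3.2.4 is worded as a definition, a patient is excluded only if (pressure above 150/90 on both readings) AND (at least two antihypertensives). The pressures below are illustrative and do not come from the documents.

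| Screening pressure | Antihypertensives | Above 150/90? | Two or more drugs? | Excluded by 3.2.4? |
|---|---|---|---|---|
| 155/95 | 2 | yes | yes | yes |
| 155/95 | 1 | yes | no | no |
| 175/105 | 1 | yes | no | no |
| 175/105 | 0 | yes | no | no |

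The first and third rows also show the rule working backwards. A patient at 175/105 on one drug is not excluded. If a second drug brings the pressure down to 155/95, the patient has improved and is now excluded, with no waiver available.

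**Step 2: does another entry criterion supply a limit?**

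- 3.1.10 (organ and marrow function): hematological, renal, hepatic and coagulation limits only.
- 3.2.7 (recent cardiac and vascular events): hypertension is not listed.
- 3.1.8: reaches high pressure only if it is a toxicity of earlier treatment, and exempts events judged clinically non-significant or stable on supportive therapy. It has no pressure threshold.
- 3.2.14: the investigator may exclude, but is not required to, and no threshold is given.
- 6.1, footnote 1: blood pressure is recorded, with no limit.

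None of these sets a blood pressure limit.

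**Step 3: does a rule act after dosing starts?** The non-hematological hold rules in 5.2 concern treatment-emergent toxicity, and 8.3 counts a worsening of a pre-existing condition as an adverse event. A rise in pressure on treatment can therefore be acted on under these sections. A high entry pressure that stays the same triggers neither. Section 5.6 does allow withdrawal at the investigator's discretion for safety, or when the treating physician finds continuation not in the patient's best interest. That route is discretionary, not automatic.

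**Result.** Above 150/90 on no drug or one drug, the protocol relies on discretion (3.2.14, 5.6) and, for toxicity of prior therapy only, on 3.1.8.

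**The case against.** The strongest reply is that the wording is deliberate. Pressure that stays high on two drugs is hypertension that treatment has failed to control, and the sponsor may have wanted to exclude only that. On this reading there is no contradiction: the untreated patient can still be treated. This stands as a possibility, since the documents do not say what was intended. But the protocol does not require that patient to be treated before the first dose, so even on this reading the rule leaves the higher pressure to judgment.

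The second reply is that the harm is not shown. No section says that ESK981 raises blood pressure, and hypertension is not among the phase 1 events reported in 1.2.4 and 8.1.2. The list of common events there covers only those seen in at least 20% of patients, so silence does not prove absence. The reply still stands to this extent: the documents do not quantify the risk.

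Three stronger readings are tempting and are not supported.

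- A reader might infer that the protocol admits these patients. It only fails to exclude them on pressure; 3.2.14 is still available.
- A reader might infer that nothing in the protocol can act on a stable high pressure. Section 5.6 can, at the investigator's discretion.
- A reader might take the 28 days from C1D1 to the next scheduled vital signs, or the 20 ESK981 doses between them (5 per week x 4 weeks), as the size of the problem. Those figures describe visit spacing and are the same for a patient who enters with normal pressure. They do not measure an eligibility gap.

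**Conclusion.** The point holds as a defect in the wording of an eligibility rule. As written, 3.2.4 and the synopsis apply the 150/90 limit only to patients on two or more antihypertensives, and no other criterion sets a limit for the rest. The rule therefore works against its evident safety purpose and should be corrected.

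The size cannot be given. The documents contain no baseline blood pressure data and no estimate of how many candidates would be above 150/90 on fewer than two drugs, so neither the number of patients nor the clinical risk can be derived. The primary endpoint, the response boundaries and the error rates of the Simon design do not depend on this criterion.

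The conclusion assumes that sites apply the criterion literally, as the no-waiver rule suggests. Confidence is moderate, because the intention may have been to exclude resistant hypertension only.

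**What to change.** In 3.2.4 and the synopsis, remove the drug-count condition: exclude pressure above 150/90 on two screening readings taken an hour or more apart, whatever the number of antihypertensives. State that antihypertensive treatment may be started or adjusted and the pressure re-measured within the day -28 to -1 window, and that the last qualifying readings decide eligibility. Nothing in the current text bars this re-measurement, but saying so keeps the stricter limit from losing patients who can be controlled. If the sponsor does mean to exclude only resistant hypertension, the text should say that.

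The cost is a few sentences and no new visit. A few patients would wait for control, and the drug chosen must not be one barred by 3.2.12; Appendix 2, for example, lists diltiazem as a CYP3A4 inhibitor.

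An optional addition, separate from the correction, is to apply the same limit to the C1D1 vital signs already scheduled, taken before the first dose. Any delay would have to fit the rule in 5.1: "Protocol treatment must start within 14 business days of enrollment to the study".
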